7.5 Exclusion Criteria

If **ANY** of the exclusion criteria are met, the Subject is excluded from the study.

- 1. Subject is unable to read English or Spanish.
- 2. Subject has dementia or lacks capacity for self-care.
- 3. Life expectancy less than 12 months from first study procedure.
- 4. Subject unable to understand or cooperate with hemodialysis nurse and dialysis care team.
- 5. Subject has a documented history of non-adherence to dialysis therapy that would prevent successful completion of the study.

- 6. Subject has had a recent major cardiovascular adverse event within the last 3 months.
- 7. Subject has New York Class III or IV Congestive Heart Failure, or ejection fraction less than 30%.
- 8. Subject has a persistent pre-dialysis sitting systolic blood pressure less than 100 mmHg despite medical therapy.
- 9. Subject has symptomatic intra-dialytic hypotension requiring medical intervention in two of their last three treatments.
- 10. Subject has an active infection requiring antibiotics within last 7 days.
- 11. Subject with fluid overload due to intractable ascites secondary to liver cirrhosis.
- 12. Subject has uncontrolled blood pressure (e.g. sustained/persistent pre-dialysis systolic blood pressure greater than 180 mmHg despite maximal medical therapy in two of the last three treatments).
- 13. Subject is intolerant to heparin.
- 14. Subject is seroreactive for Hepatitis B Surface Antigen.
- 15. Subject has an active, life-threatening, rheumatologic disease.
- 16. Subject has a history of adverse reactions to dialyzer membrane material.
- 17. Subject is participating in another investigative drug or device clinical study related to Home Hemodialysis which conflicts with the execution of this study.
- 18. Subject is expected to receive an organ transplant during the course of the investigation.
- 19. Subject has a life-threatening malignancy actively receiving treatment that would prevent successful completion of the study protocol.
- 20. Any other documented condition that the Investigator feels would prevent the Subject from successful inclusion in the study.

7.6 Subject Discontinuation and Replacement

Every Subject should remain in the study until completion of the required follow-up period. Subjects may voluntarily withdraw from the study at any time with or without reason and it will not have any negative impact on subsequent treatment. Conceivable reasons for Subject discontinuation may include, but are not limited to, the following:

- **Subject Withdrawal:** Subject participation in this clinical study is voluntary. The Subject may choose to discontinue participation (refuse all subsequent testing) at any time without loss of benefits or penalty.
- **Discontinuation:** Subject participation may be discontinued by the Subject or Investigator because of a treatment modality change, organ transplant, transfer, death or prolonged hospitalization.
- **Investigator Termination:** The Investigator may terminate the Subject's participation without regard to the Subject's consent if the Investigator believes it is medically necessary.
- Exclusion Criterion Discovered After Enrollment: A small number of Subjects may be enrolled despite meeting an exclusion criteria due to timing of study required clinical procedures. This will be documented by the study personnel on the Case Report Form (CRF), and will be considered a protocol deviation.

- Lost-to-Follow-up: If the Subject fails to complete eight consecutive treatments, regardless of whether or not they fall into a single treatment period or a total of up to eight missed treatments, consecutive or not, per period, but has not formally withdrawn from the study, he or she will be considered lost-to-follow-up. The data from this Subject is still eligible for the intent to treat dataset. Site personnel should make all reasonable efforts to locate and communicate with the Subject, at each contact time point, including:
 - A minimum of two telephone calls to contact the Subject should be attempted. Each attempt should be recorded in the Subject's medical record, including date, time, and initials of site personnel attempting the contact.
 - o If telephone calls are unsuccessful, a certified letter should be sent to the Subject.

If the above-mentioned attempts at communicating with the Subject are unsuccessful, the Subject will be considered lost-to-follow-up.

NOTE: If the Subject can be contacted, study treatments will resume at the point when the last treatment was conducted.

In all cases, the reason(s) for withdrawal, if given, must be recorded on the appropriate CRF and in the Subject's medical record. If more than one reason is cited for withdrawal, study personnel must identify the most significant reason and record this reason on the CRF. Investigators must also report all Subject withdrawals to their IRB as defined by their institutions' procedures. Subjects who withdraw or are withdrawn from the study, or are lost to follow-up may be replaced.

8 STUDY PROCEDURES

8.1 Baseline Evaluation

The baseline evaluation will include, but is not limited to, the following testing and assessments, and will be conducted prior to initiating the Run-In period per Appendix B:

- Documentation of consent
- Demographics (Sex, Age, Ethnicity, Race)
- Physical Examination
- Medical History (including history of vascular access)
- Hemodialysis prescription (e.g., equipment, number of times dialyzed per week, and whether inhome or in-clinic settings)
- Laboratory Values
 - Documentation of Laboratory values for 3 months prior to Run-In.
 - Laboratory Testing (hematology and chemistry) as needed*
- Assessment of kinetics
- Routine signs and symptoms
- Concomitant medications

* If the subject has had lab work within two weeks of the run-in period that contains all of the protocol specified tests, a repeat lab draw at baseline is not necessary.

If, after completion and review of the above data, the Subject appears to be a good candidate for study enrollment and is assessed as being able to perform self-care, the Investigator will proceed with the runin period using the Tablo Hemodialysis System.

8.2 1-week Run-in

The 1-week run-in period will include, but is not limited to, the following testing, procedures, and assessment per Appendix B:

- Subject's Dialysis Prescription Settings
- Pre-dialysis vitals, including body weight, temperature, blood pressure, and heart rate (pulse)
- Number of dialysis sessions completed
- Post-Dialysis body weight
- Assessment of Kinetics
- Concomitant Medications
- Assessment of dialysis interval adverse events (if any)
- Final assessment of Subject eligibility

All treatments will be performed using the Tablo[™] Hemodialysis System. Dialysis personnel, trained on the use of the device, will input the dialysis prescription as detailed below:

The dialysis prescription will include:

- Access blood flow (set between 300 and 400 ml/min.)
- Dialysate temperature (between 36 and 39 degrees Celsius adjustable by 0.5 degrees increments)
- Composition of dialysate: potassium (limited to 2 mEq/dL versus 3 mEq/dL), bicarbonate (30 to 40 mEq/L adjustable in 1 mEq/L intervals), sodium concentrations (135-145 mEq/L in 1mEq/liter increments)
- Treatment length in minutes between 160 minutes and 240 minutes
- Blood pressure parameters for ultrafiltration
- Heparin dose and anticoagulation parameters

Using established center protocols, and after adequate patient training for performing their own first cannulation, dialysis personnel will observe or perform: 1) the Subjects' dialysis access (i.e., catheter, fistula or graft) preparation using In-Center aseptic technique, and 2) cannulation of the fistula or graft, or connection to a catheter. Dialysis will then be initiated and ongoing monitoring of the Subject will be done per center protocol. During treatment, vital signs, including blood pressure measurements and heart rate (pulse), will be collected every 30 minutes for the first hour, then hourly until the completion of the treatment.

Post-treatment vitals, including body weight, temperature, blood pressure and heart rate (pulse), will also be collected.

Each Subject will be prescribed dialysis therapy using the Tablo[™] Hemodialysis System for four times per week with no inter-dialytic (end of treatment period to start of next treatment) period greater than 2 days. No isolated ultrafiltration will be available on the device during the study.

During the Run-In period, Investigators or their designee, may use other clinical assessment indicators to determine the Subject's ability to perform self-care (including but not limited to, self-cannulation and assessment of the home environment). Any issues which would prevent dialysis from being performed, or that would require a change in dialysis procedure will be communicated to Outset.

If, after completion of the baseline evaluation and Run-In period, the Investigator determines the Subject meets all inclusion and exclusion criteria, the Subject will begin Treatment Period 1, In-Center dialysis using the Tablo Hemodialysis System.

8.3 Treatment Period 1 (In-Center)

Investigators or their designee will perform routine pre-dialysis assessment of adverse events, infections, medication changes, and subject's vitals including body weight, blood pressure, temperature, and heart rate (pulse). Any issues which would prevent normal dialysis from being performed or that would require a change in dialysis procedure will be communicated with the study Sponsor.

Dialysis personnel, trained on the use of the device, will perform device set-up, input the dialysis prescription and administer dialysis therapy In-Center during Treatment Period 1 according to the Investigator's instruction.

Prior to treatment, pre-dialysis vitals, including body weight, temperature, blood pressure, and heart rate (pulse), will be collected. Using established center protocols, dialysis personnel will observe or perform: 1) the Subjects' dialysis access (i.e., catheter, fistula or graft) preparation using In-Center aseptic technique, and 2) cannulation of the fistula or graft, or connection to a catheter. Dialysis will then be initiated and ongoing monitoring of the Subject will be done per center protocol. During treatment, vital signs, including blood pressure measurements and heart rate (pulse), will be collected every 30 minutes for the first hour, then hourly until the completion of the treatment.

Post-treatment vitals, including body weight, temperature, blood pressure and heart rate (pulse), will also be collected.

NOTE: Subjects are considered enrolled in the Study if they have met all inclusion and exclusion criteria and the first treatment during Treatment Period 1 has been started.

Each Subject will be prescribed dialysis therapy for four times per week with no inter-dialytic (end of treatment period to start of next treatment) period greater than 2 days. No isolated ultrafiltration will be available on the device during the study.

During therapy, each Subject is encouraged to limit food and water intake. Subjects will document any alarms that occurred which required intervention (such as medication or saline administration or a change in treatment parameters), under what conditions they occurred, and final resolution. A summary of alarm occurrence will be tabulated from data transmitted to Outset Medical. Subjects will also document any signs or symptoms that they experienced during treatment.

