5.2 Evaluation of Safety

The primary safety endpoint will be calculated using the mean number of adverse events from the prespecified list observed during a dialysis interval as follows:

- 1. Serious Adverse Event: any serious adverse event that:
 - Results in death,
 - Is life-threatening,
 - Requires hospitalization or prolongs existing hospitalization,
 - Requires intervention to prevent permanent impairment or damage, or
 - Results in persistent or significant disability/incapacity.
- 2. Allergic Reaction: Type A, anaphylactoid or Type B dialyzer reactions to dialyzer, blood tubing or chemical disinfectant.
- 3. **Blood Loss**: blood loss resulting in hemodynamic compromise that leads to death, transfusion or fluid resuscitation with greater than 1 liter of crystalloid IV fluids.
- 4. **Hemolytic Reaction**: hemolytic reactions due to disinfectant exposure, dialysate temperature, mechanical failure or other device related causes.
- 5. Infection: any infection related to catheter, its tunnel or exit site, AV fistula, or AV graft.
- 6. Intra-Dialysis Event: a significant clinical event such as loss of consciousness, cardiac arrest, or seizure caused by device failure.
- 7. Vascular Access Complication: defined as AVF or AVG clotting during the dialysis procedure, bleeding for more than 30 minutes post-dialysis for 3 consecutive sessions, difficulty with vascular access resulting in inability to initiate or complete dialysis treatments or complications related to hemodialysis catheters (not including reduced blood flow in catheter or TPA or catheter exchange).
- 8. **Pyrogenic Reaction**: onset of objective chills (visible rigors) and fever (oral temperature greater than or equal to 37.5 degrees Celsius) in a Subject who was afebrile and who had no recorded signs or symptoms of infection before treatment.

A dialysis interval is defined as the start of one dialysis treatment until the start of the next dialysis treatment. The primary safety analysis will be performed on the Intent-to-Treat (ITT) population.

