8.5 Treatment Period 2 (In-Home dialysis treatment)

Subject will administer dialysis therapy at home during Treatment Period 2 according to the Investigator's instruction. After device setup, the Subject will take his/her pre-dialysis vitals, including body weight, temperature, blood pressure, and heart rate (pulse), and confirm the dialysis prescription.

Using established center protocols, the subject or identified trained individual will: 1) prep Subject's dialysis access (i.e., catheter, fistula or graft) using trained aseptic technique, and 2) perform cannulation of the fistula or graft, or connection to a catheter.

Once all pre-treatment steps are complete, the Subject will initiate dialysis and monitor their treatment according to the center protocol. During treatment, vital signs, including blood pressure measurements and heart rate (pulse), will be collected every 30 minutes for the first hour, then hourly until the completion of the treatment.

Post-treatment vitals, including body weight, temperature, blood pressure and heart rate (pulse), will also be collected.

During therapy, each Subject is encouraged to limit food and water intake. Subjects will document any alarms that occurred which required intervention (such as medication or saline administration or a change in treatment parameters), under what conditions the alarms occurred, and final resolution. A summary of alarm occurrence will be tabulated from data transmitted to Outset Medical. Subjects will also document any signs or symptoms that they experienced during treatment.

Each Subject will be prescribed dialysis therapy for four times per week with no inter-dialytic (end of treatment period to start of next treatment period) period greater than 2 days. No isolated ultrafiltration will be available on the device during the study.

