8.6 Weekly Visits during the In-Center and In-Home Treatment Periods

Weekly visits for each Subject will be conducted by a study staff member during Treatment Periods 1 (In-Center) and 2 (In-Home). During this weekly visit, signs and symptoms experienced by the Subject both since the last dialysis treatment as well as those experienced during dialysis treatments will be reviewed, as well as compliance to treatment time. The study staff member will also review the definitions of adverse and serious adverse events and re-educate the Subject where necessary.

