9.2 Recording Adverse Events

9.2.1 Adverse Event Categorization

Reported Adverse Events will be categorized into one of the following two categories:

- 1. Primary Safety Endpoint: This category includes the 8 pre-specified adverse events that will be analyzed as the Primary Safety Endpoint for the study.
- 2. Other Adverse Events: This category includes all reported adverse events that meet the definition in Section 9.

The proposed categorization will serve to focus reporting, adjudicating, and analysis efforts to those categories most relevant for demonstrating the investigational device's relevant safety profile.

It is the intention of the Sponsor that AE's be collected in a uniform manner over the course of the study (independent of study arm) through the use of a Subject questionnaire. The Subject will be asked to complete a questionnaire regarding signs and symptoms experienced during each treatment. During regularly scheduled clinical follow-up visits during the trial, study staff will review the signs and symptoms noted by the Subject and provide education, as needed, on how they are documented. The study staff will determine whether subject reported signs and symptoms meet the definition of an AE as specified in Section 9. This approach attempts to eliminate any potential observed differences in AE rates between the study arms that are solely due to reporting sources or techniques.

Prior to analysis, all adverse events (AEs) will be coded using the Medical Dictionary for Regulatory Activities (MedDRA). Based on these coded terms, treatment emergent AEs will be summarized by treatment period, by severity, relation to procedure and relation to device.

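### The questionnaire meant to make AE capture uniform covers only time on dialysis, and only the In-Center period adds a routine staff pre-dialysis check, so between-treatment events at home may be under-counted

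*Protocol*

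**What the plan says.** **Aim.** Protocol 9.2.1 states the sponsor's intention: "AE's be collected in a uniform manner over the course of the study (independent of study arm) through the use of a Subject questionnaire". Its stated reason is this: "This approach attempts to eliminate any potential observed differences in AE rates between the study arms that are solely due to reporting sources or techniques".

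**Instrument.** The same section defines its scope: "The Subject will be asked to complete a questionnaire regarding signs and symptoms experienced during each treatment". Protocol 8.10 describes the questionnaire in the same terms.

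**Endpoint window.** Protocol 5.2 counts pre-specified events per dialysis interval: "A dialysis interval is defined as the start of one dialysis treatment until the start of the next dialysis treatment". SAP 5.1 divides that interval into treatment, interdialytic and pre-treatment parts, and all three count.

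**In-Center.** Protocol 8.3 adds: "Investigators or their designee will perform routine pre-dialysis assessment of adverse events, infections, medication changes, and subject's vitals". Staff also observe or perform access preparation and cannulation, so they see the access site.

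**In-Home.** Under Protocol 8.5 the subject takes his or her own vitals, and the subject or the trained individual prepares the access. No staff check of adverse events, infections or medication changes is listed.

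**Both periods.** Protocol 8.6 gives a weekly staff visit. It reviews symptoms during treatments and symptoms since the most recent treatment.

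**The concern.** Only the In-Center period has a listed staff step that can pick up, before the next treatment, events that arose since the last one. At home the same events depend on the subject volunteering them or on the weekly visit. The difference in reporting source that 9.2.1 sets out to remove is therefore built into 8.3 and 8.5.

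Two things are at stake. SAP Table 16 prints the In-Center and In-Home rates one above the other, and Protocol 6.3 describes the study as a comparison of the two settings, so readers will compare them. In addition, Protocol 11.3 makes success depend on estimating each period's rate to a set precision. Recording fewer events makes that criterion easier to meet.

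**Working it through.** The point rests on the text and on no stated figure. The arithmetic below only gives scale.

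**1. Share of the week the questionnaire covers.** Inputs: 160 to 240 minutes per treatment (Protocol 8.2), 4 treatments per week, 168 hours per week.
- 4 × 160/60 = 10.7 h; 10.7/168 = 6.3%
- 4 × 240/60 = 16.0 h; 16.0/168 = 9.5%

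This gap is the same in both periods. By itself it creates no difference between them.

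**2. Scheduled staff AE contacts per subject per period.** Inputs: 32 treatments and about 8 weekly visits. Assumption: the routine check in 8.3 is done at every treatment.
- In-Center: 32 + 8 = 40 (5 per week)
- In-Home: 8 (1 per week)

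**3. Look-back of the weekly visit.** Read literally, 8.6 reaches back to the most recent treatment. With four treatments a week that is about one of four between-treatment gaps, leaving 3/4 outside the stated window.

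**4. Range for the recorded home rate.** Suppose the true rates are equal and capture is complete In-Center, on dialysis and in the covered gap. Let f be the share of events arising between treatments and c the chance that an event in the other three gaps is recorded at home. Both are assumptions; the documents give neither.

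Ratio of recorded In-Home to In-Center rate = 1 − f × 0.75 × (1 − c)

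| f | c = 0 | c = 0.5 | c = 1 |
|---|---|---|---|
| 0.25 | 0.81 | 0.91 | 1.00 |
| 0.50 | 0.63 | 0.81 | 1.00 |
| 0.75 | 0.44 | 0.72 | 1.00 |

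The right-hand column matters: if the other routes work at home, nothing is lost.

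**5. Effect on the precision criterion.** Protocol 11.8 wants a 95% half-width below 1 per 100 treatments with 30 subjects × 32 treatments. Its own inputs (SD 0.8, AR(1) correlation 0.50) do not reproduce that. The variance of a subject's mean is 0.8²/32² × [32 + 2 × Σ(32 − k) × 0.5^k] = 0.0575, so the half-width is 1.96 × √(0.0575/30) = 0.086, or 8.6 per 100. That is a separate matter and does not decide this point.

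The planned model is Poisson, where the variance follows the rate. As a simplification, take 30 × 32 = 960 independent treatments, so half-width = 1.96 × √(rate/960).
- The criterion is just met at rate = (0.01/1.96)² × 960 = 0.025, or 2.5 per 100.
- True rate 5 per 100, fully captured: half-width 1.41, not met.
- Captured at ratio 0.81 (4.06 per 100): 1.27, still not met.
- Captured at ratio 0.44 (2.19 per 100): 0.94, met.
- True rate 2 per 100, fully captured: 0.89, met in any case.

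Missed events always push towards meeting the criterion, but they change the outcome only for some rates and only if the loss is large.

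**The case against.** **The plan does schedule AE recording at home.** SAP 1.2 lists adverse events at every treatment in each of the four periods, and Appendix B has an AE row running through both treatment periods. Protocol 12.2 has the CRF collect adverse events and hospitalizations since the prior visit. Protocol 9.2.2 requires monitoring throughout, and 9.3 requires SAEs to be reported at once on awareness. This stands in part: capture at home is not confined to the weekly visit. But SAP 1.2 names no assessor and no look-back. The Appendix B row cites footnote 13, a list of laboratory tests. Section 12.2 gives a window for the form without saying who asks at home, or when. The 9.3 duty starts only once someone knows. The Clinical Events Committee rules on reported events and cannot recover missed ones.

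**Much of the composite is not exposed.** This stands. Deaths and hospitalizations have other routes. Clotting during the procedure, inability to start or finish treatment, and intra-dialysis events show themselves on dialysis. Prolonged bleeding counts only if it recurs over 3 consecutive sessions, which at four sessions a week spans much of a week and is less likely to escape a weekly visit. Home subjects also take their temperature before and after each treatment.

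**No between-period safety test is planned, and the shift may be small.** The first part stands. On the second, assume 3 events per 100, half of them between treatments, with 60 to 90% of those captured at home. The rate then reads 3 × (0.5 + 0.5 × 0.6) = 2.40 to 3 × (0.5 + 0.5 × 0.9) = 2.85, a shift of 0.15 to 0.60, inside the planned half-width of 1. With f = 0.5 and c = 0 it reads 3 × 0.625 = 1.875, a shift of 1.125. Either result follows from the assumption chosen.

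**Staff presence is part of what distinguishes the settings, and 9.2.1 states an aim only.** Fair, but asking the subject the same questions over the same window in both periods needs no staff presence.

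**Conclusion.** The documents show unequal scheduled ascertainment: a routine staff pre-dialysis AE and infection check In-Center, none listed at home, and a common questionnaire that omits the time between treatments. This conflicts with the aim of 9.2.1. The likely direction is a lower recorded In-Home rate, mainly for access infections and milder access problems.

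A reader might infer that home events are in fact under-counted, by some stated percentage, or that the safety comparison fails. The documents do not support that. They contain no capture data, they provide other recording routes at home, and they plan no between-period test. Under the assumptions in the working, the recorded home rate could lie anywhere from 0.44 to 1.00 of an equal In-Center rate, so the size is undetermined. The contact count of 40 against 8 also assumes that the routine check is done at every In-Center treatment.

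This is a cheap improvement worth making, because the rates are displayed together and under-capture would ease a success criterion. It does not invalidate the safety endpoint.

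**What to change.** 1. **Protocol 9.2.1 and 8.10.** In both treatment periods, have the subject answer before each treatment for the whole time since the previous treatment started (fever or chills, access redness or discharge, prolonged bleeding, hospital or urgent visit), as well as for the treatment itself.
2. **Protocol 8.6.** Reword so that the weekly review covers every dialysis interval since the prior weekly visit.
3. **Appendix B.** Reconcile the footnote on the AE row. Footnote 12 carries the recording-at-every-treatment text; footnote 13 is a laboratory list.
4. **Optional.** Add a source-of-detection field to the AE CRF, for description only. Do not report a rate restricted to sources common to both periods. A first-source field would drop In-Center events found at the pre-dialysis check that the weekly visit would also have found, and so bias the comparison the other way.

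**Cost.** A few more questions on a form already completed at every treatment, wording changes in the protocol and, if wanted, one CRF field. No extra visits or staff. Subjects carry a small added burden, and the In-Home rate may rise slightly.
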